- j. Dipstick urinalysis will be completed by the sites at all required visits. A microscopic analysis will be performed by the central laboratory, in the event the dipstick results show protein, ketones or blood greater than negative or glucose greater than normal.
- k. All females of childbearing potential will have a serum pregnancy test at Weeks 48, 96, 144, 192, 240 and 288/Premature Discontinuation Visit.
- 1. At Week 4 visit and all subsequently scheduled study visits, all females of childbearing potential will have a urine pregnancy test performed locally by designated study personnel. If any urine pregnancy test is positive, a serum pregnancy test will be performed by the central laboratory. Any subject with a positive urine pregnancy test must have a negative serum test performed at the central laboratory prior to enrollment or continuation in the study.

[figure not shown]
[figure not shown]

Table 1. Study Activities (Continued)

- m. IMPACT III Quality of Life questionnaire at Weeks 24, 48, 72, 96, 120, 144, 168, 192, 216, 240, 264 and 288/Premature Discontinuation Visit will be completed for subjects 9 years of age or older at the baseline study visit.
- n. WPAI will be completed by subject's parent or legal guardian at Weeks 24, 48, 72, 96, 120, 144, 168, 192, 216, 240, 264 and 288/Premature Discontinuation Visit. The questionnaire will not be completed if the subject's parent or legal guardian is not taking care of the subject anymore.
- o. If the height velocity is 0 and, in the opinion of the investigator, a subject is no longer growing, the x-ray for bone age can be omitted. Assessment of bone age is not required for subjects at the Premature Discontinuation Visit.
- p. Collection of SAEs begins the day the subject signs the informed consent.
- q. Subjects will be dispensed a subject diary at Baseline and will be trained on how to complete the diary by site staff during the Baseline visit. All subjects should complete their subject diary on a daily basis throughout the entire study, including if and when hospitalized whenever possible. The diary will be reviewed by site personnel with the subject at each visit and collected at the Week 288/Premature Discontinuation Visit.
- r. Study drug may be dispensed at the Unscheduled Visit if there is a change in the dosing schedule (i.e., subject meets criteria of disease flare) or if damaged drug needs replacement.

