The Mayo Score (consisting of the Partial Mayo Score plus the endoscopic subscore) will be calculated at weeks where endoscopy is performed (i.e., Week 48, 96, 192 and 288). The Partial Mayo Score and the Mayo Score (consisting of the Partial Mayo Score plus the endoscopic subscore) assessed at the Week 52 visit of Study M11-290 will be used for the Baseline assessment (prior to receiving study drug). The Mayo Score and the Script for collection of Mayo Score are described in Appendix D.

[figure not shown]
The average stool frequency subscore, rectal bleeding subscore, Partial Mayo score and Mayo score for each study visit will be recorded in the eCRF in decimal numbers.

For the purpose of disease flare assessment, Baseline PMS will be rounded up or down to the nearest full number. For example, if a patient had a PMS of 5.4 at Baseline and came in for a disease flare assessment, then the Baseline PMS would be rounded down to 5.0 for this purpose. If a patient had a PMS of 5.5 at Baseline and came in for a disease flare assessment, then the Baseline PMS would be rounded up to 6.0.

Whenever possible, the same physician (investigator or subinvestigator) should determine all Mayo Scores and Partial Mayo Scores for an individual subject through the duration of the study.

IMPACT III Questionnaire²²

Subjects 9 years of age or older at Baseline will complete an IMPACT III questionnaire at Baseline, Weeks 24, 48, 72, 96, 120, 144, 168, 192, 216, 240, 264, and 288/Premature Discontinuation Visit.

The IMPACT III questionnaire assessed at the Week 52 visit of Study M11-290 will be used for the Baseline assessment (prior to receiving study drug).

WPAI Questionnaire

Work Productivity and Activity Impairment Questionnaire (WPAI) will be completed at Baseline, Weeks 24, 48, 72, 96, 120, 144, 168, 192, 216, 240, 264, and 288/Premature Discontinuation Visit (Appendix E). The WPAI questionnaire assessed at the Week 52 visit of Study M11-290 will be used for the Baseline assessment (prior to receiving study drug).

[figure not shown]
The subject's parent or legal guardian will complete the WPAI. The questionnaire will not be completed if the subject's parents or legal guardian do/does not take care of the subject anymore.

States of Emergency or Pandemic-Related Acceptable Protocol Modifications

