All time points and corresponding time windows are defined based on Rx days. The protocol specified visits and corresponding time windows are presented in the table below. Measures will only be displayed at the visits where they were planned to be measured. For example, Mayo score is collected at Weeks 0, 48, 96, 192 and 288/Premature Discontinuation (dependent on availability of optional endoscopy data at these timepoints).

Assigned Visit	Nominal Day	Time Window (Rx Day Range)
Week 0	1	≤ 1
Week 4	29	2 to 43
Week 8	57	44 to 71
Week 12	85	71 to 127
Week 24	169	128 to 211
Week 36	253	212 to 295
Week 48	337	296 to 379
Week 60	421	380 to 463
Week 72	505	464 to 547
Week 84	589	548 to 631
Week 96	673	632 to 715
Week 108	757	716 to 799
Week 120	841	800 to 925
Week 144	1009	926 to 1093
Week 168	1177	1094 to 1261
Week 192	1345	1262 to 1429
Week 216	1513	1430 to 1597
Week 240	1681	1598 to 1765
Week 264	1849	1766 to 1933
Week 288	2017	1934 to 2101

If more than one assessment is included in a time window the assessment closest to the nominal day should be used. If there were more than one observation with equal distance to the nominal day the latest one will be used in analyses. For any given variable, if more

than one measurement exists for a subject on the same day, the average of the measurements will be considered to be that subject's measurement for that day.

Missing Data Handling

In general, missing Baseline and safety data will not be imputed.

Baseline Value is Missing:

Subjects will be excluded from analysis of change from Baseline if Baseline evaluation is missing.

Missing Efficacy and Outcome Evaluations:

The following methods will be used for imputing missing values to perform the efficacy analyses.

[figure not shown]
For interim analyses, missing values will only be imputed up to the timepoint a patient could have potentially reached at the data cutoff for analyses.

Observed Cases (OC): missing values will not be used for the observed case analysis.

Last Observation Carried Forward (LOCF): For categorical and continuous efficacy variables the following rules will be used for LOCF approach:

- Baseline and pre-baseline values will not be used to impute the missing post-baseline values, and
- Missing values after baseline will be imputed using the last non-missing values after baseline and prior to the missing value.

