When calculating **IMPACT III** total score, if 4 or more of the items are missing then IMPACT III total score and all subscores will be considered missing. Otherwise, if there are 3 or fewer missing answers, the average of non-missing values will be used to replace the missing items for the total score and subscore calculation. If for subscores consisting of only 3 items (see 'Score Definitions' later in this Section), all of these items are missing and are replaced per above convention, a footnote will be added indicating for how many subjects the subscore included in the analysis has been fully imputed.

When calculating the **WPAI** scores, the following computational notes should be followed.

- Define Employment as a binary YES or NO variable where YES corresponds to "Employed" and NO corresponds to "Not Employed":
 - A subject will be considered EMPLOYED at a given visit if Q1 = YES or Q2 > 0 or Q4 > 0.
 - A subject will be considered UNEMPLOYED at a given visit if Q1 = NO and no positive hours recorded under Q2 and Q4 (i.e., if Q1 = NO AND $Q2 \le 0$ AND $Q4 \le 0$, then UNEMPLOYED).
 - Employment status for a subject will be considered missing at a given visit if Q1 = missing and no positive hours recorded under Q2 and Q4.
- If a subject is UNEMPLOYED or employment status is missing, then S1, S2, and S3 will be set to missing.
- If Q2 = 0 and Q4 = 0 or missing then Q2/(Q2 + Q4) = missing (i.e., S1 = missing).
- If Q2 = 0 and Q4 = 0, then set S3 to missing.
- If Q2 is missing or Q4 is missing, then set S1 and S3 to missing.
- If Q4 = missing, then DO NOT set Q5 = missing.
- If Q5 is missing, then apply the following rules:
 - \circ If Q2 > 0, Q4 = 0, and Q5 = missing, then S3 = 100%.
 - \circ If Q2 = 0, Q4 > 0, and Q5 = missing, then S3 is missing.
 - \circ If Q2 > 0, Q4 > 0, and Q5 = missing, then S3 is missing.
- Determine if a subject missed work (based on Q2) in order to analyze the proportion of subjects who missed work:
 - Create a binary (YES or NO) "missed work" variable.
 - A subject will be considered as yes to missed work if Q2 is greater than 0.
 - If Q2 = missing, then MISSED WORK = missing.
 - \circ If Q2 > 0, then MISSED WORK = YES
 - \circ If Q2 = 0, then MISSED WORK = NO

• Therefore, the proportion of subjects who missed work will be counted based on the number of subjects with MISSED WORK = YES.

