10.1 General Considerations

No confirmatory testing for efficacy endpoints will be performed in this open-label study.

[figure not shown]
Endpoints that are of the binary type will be analyzed as proportions including 95% CIs. Endpoints that are of the continuous type will be analyzed as changes from baseline, and reported including 95% CIs. OC and LOCF (see Section 6.0) will be used, unless otherwise noted.

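### The SAP's LOCF rule refills WPAI work scores that do not apply because the caregiver has stopped working or stopped caregiving

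*SAP*

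**What the plan says.** **When a work score is blank.** The WPAI notes in SAP Section 6.0 state: "If a subject is UNEMPLOYED or employment status is missing, then S1, S2, and S3 will be set to missing". S1 is absenteeism, S2 presenteeism and S3 overall work impairment. The fourth score, S4 (activity impairment), does not depend on having a job.

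**When the whole questionnaire is blank.** Footnote n to Table 1 of the protocol says: "The questionnaire will not be completed if the subject's parent or legal guardian is not taking care of the subject anymore". The WPAI paragraph of protocol Section 5.3.1.1 repeats this. From then on S1 to S4 are all blank.

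**What happens to blanks.** SAP Section 10.2 lists change from Baseline in the WPAI scores as an efficacy endpoint. Section 10.1 sets the default: "OC and LOCF (see Section 6.0) will be used, unless otherwise noted". Section 6.0 introduces the LOCF rules with "For categorical and continuous efficacy variables the following rules will be used for LOCF approach" and then says: "Missing values after baseline will be imputed using the last non-missing values after baseline and prior to the missing value". Baseline values may not be carried, and subjects without a Baseline value are left out of change from Baseline. No WPAI exception is noted in any of these places.

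**The concern.** A work-impairment score for someone without a job is undefined; it is not an unobserved quantity waiting to be estimated. The SAP recognises this when it blanks S1 to S3. However, it uses one code, missing, for two different things: a value that exists but was not reported, and a value that does not exist. LOCF cannot tell them apart, so a programmer who follows the text literally will undo the blanking rule and enter impairment at a job the caregiver no longer holds. After caregiving ends, the same happens to all four scores.

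At stake is how the LOCF display of a caregiver-reported endpoint is read. Its mean would mix current impairment with outdated scores. A difference between the LOCF and observed-case tables could come from dropout or from these refilled cells, and the reader could not say which.

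**Working it through.** **1. Visit schedule.** The SAP 6.0 window table gives nominal day = 7 × week + 1. Week 24: 7 × 24 + 1 = 169. Week 288: 7 × 288 + 1 = 2017. Both match the table.

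**2. Eligible donors.** Table 1, footnote n, gives the WPAI visits: "WPAI will be completed by subject's parent or legal guardian at Weeks 24, 48, 72, 96, 120, 144, 168, 192, 216, 240, 264 and 288/Premature". That makes 12 scheduled visits after baseline. Because Baseline is not carried, the earliest scheduled donor is Week 24.

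**3. Longest carry.** (2017 − 169) / 7 = 264 weeks. A score seen only at Week 24 can fill 12 − 1 = 11 later visits, Weeks 48 to 288. This is a ceiling. At an interim analysis SAP 6.0 stops imputation at the time point the patient could have reached, so the span is then shorter.

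**4. Who can be affected.**
- No score at Baseline: excluded from change from Baseline, so no effect.
- Score at Baseline but none afterwards: nothing to carry, so no effect.
- Score at Baseline and at least one later visit, then unemployed: S1 to S3 are refilled; S4 is still observed.
- Score at Baseline and at least one later visit, then caregiving ends: every WPAI score with such a history is refilled.

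**5. Size of the error.** Let q be the share of the LOCF denominator made up of refilled cells at a visit, m_c their mean change from Baseline and m_a the mean change among the rest. The LOCF mean is (1 − q) × m_a + q × m_c, which differs from m_a by q × (m_c − m_a). The documents give none of the three quantities, so neither the size nor the sign follows from them.

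**6. Illustrative counts (shares assumed).** SAP Section 4.3 expects 55 subjects outside Japan. Suppose all are followed to Week 288, between 50% and 90% have a caregiver with work scores at Baseline and Week 24, and 10% to 50% of those later become not applicable.
- Lowest: 55 × 0.5 × 0.1 = 2.75, about 3 refilled values at Week 288 in an LOCF denominator of 55 × 0.5 = 27.5, about 28.
- Highest: 55 × 0.9 × 0.5 = 24.75, about 25 refilled values in a denominator of 55 × 0.9 = 49.5, about 50.

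The width of this range shows how little the documents settle about the number affected.

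**The case against.** The strongest reply is that the observed-case analysis is planned alongside LOCF, leaves these cells out, and reports N for each summary. That is correct, and it limits the point to one of two displays. It does not settle what the LOCF display should contain.

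Protocol Section 8.1.4 describes LOCF only as an additional summary at the last visit. The SAP states no such limit, and the last visit is where the carry is longest, so the Week 288 value is refilled on either reading.

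The endpoint is descriptive, in a single-arm extension without confirmatory testing. This stands and keeps the point modest. It is also fair that carrying a score forward after a subject leaves the study is ordinary LOCF and not a WPAI defect.

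Three stronger readings are tempting, but the documents do not support them.

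- *The proportion who missed work is biased downward.* A reader might infer this from "If Q2 = 0, then MISSED WORK = NO", which carries no employment condition. But item 1 of the questionnaire (protocol Appendix E) sends a caregiver without a job straight to item 6. Q2 is then blank, and the SAP sets the missed-work variable to missing. Only a zero entered against that instruction would dilute the proportion.
- *The problem grows as subjects reach 18.* The protocol's trigger is that the parent or "legal guardian do/does not take care of the subject anymore". Age is not the trigger, and reaching adulthood does not show that care has ended.
- *LOCF overstates impairment, because a caregiver who leaves work does so with a high score.* A low score can be carried just as easily, and the endpoint is change from Baseline, not the level.

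**Conclusion.** The gap is real but narrow. As written, the SAP blanks S1 to S3 for caregivers without a job and then allows LOCF to refill them; it does the same to all WPAI scores after caregiving ends. The effect is confined to the LOCF summaries and to caregivers with a Baseline score and at least one later score who then stop work or caregiving. The carry lasts at most 264 weeks on the nominal schedule. The number affected and the direction of the error cannot be known from the documents. The conclusion assumes that the default in SAP 10.1 is applied literally to the WPAI endpoint, which is the only reading the text offers. This is a clarification worth making before programming; it does not threaten the study's main conclusions.

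**What to change.** Add to the WPAI notes in SAP 6.0, with a cross-reference from 10.1:

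- LOCF is not applied to S1, S2 or S3 at visits where the caregiver is classed UNEMPLOYED. Missing employment status stays an ordinary missing value.
- LOCF is not applied to any WPAI score after caregiving has ended.
- The LOCF table shows, per visit, the number of subjects to whom the score applies.
- If the last known status before a blank visit is UNEMPLOYED, or caregiving has ended, the score stays not applicable and no older value is used.

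As a safeguard against stray zeros only, the missed-work variable could also be restricted to caregivers classed as employed.

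**Cost.** Employment status is derived from Q1, Q2 and Q4, which are already collected, so the first rule needs only a flag in the derivation. Identifying the end of caregiving needs a recorded reason for non-completion of the questionnaire; if the case report form does not capture one, it must be added or recovered from source. LOCF denominators will be smaller wherever cells are no longer refilled. The observed-case analysis does not change.

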Subjects who have been in remission (PMS \leq 2 with no individual subscore > 1) for at least 8 weeks and for at least 2 consecutive visits may have their dosage de-escalated from ew to eow prior to Amendment 4 or to the next lower dose after Amendment 4. The investigator should receive prior approval from the medical monitor before taking any action with regard to dose de-escalation.

Subjects who demonstrate disease flare after dose de-escalation have an opportunity to re escalate their dose back to adalimumab ew dosing prior to Amendment 4 or to the next higher dose after Amendment 4. The investigator should receive prior approval from the medical monitor before taking any action with regard to dose re-escalation. One de-escalation within a period of 48 weeks and one re-escalation within a period of 48 weeks are permissible.

Methodology (Continued):

UC-related concomitant medication:

- Subjects who enroll into the study from blinded treatment in Study M11-290 will be allowed to change/initiate/discontinue their steroid dose after 4 weeks in Study M10-870.
- Subjects who enroll into the study from blinded treatment in Study M11-290 will be allowed to change/initiate/discontinue their azathioprine, 6-MP, MTX, 5-ASA doses after 8 weeks in Study M10-870.
- Subjects who enroll into the study from open label treatment in Study M11-290 will be allowed to change/initiate/discontinue their azathioprine, 6-MP, MTX, 5-ASA at any time point in Study M10-870.
- Reductions in concomitant corticosteroids, azathioprine, 6-MP, MTX, and 5-ASA will be allowed at any time in the event of moderate or severe drug-related toxicities (e.g., leukopenia, anemia, neuropathy).

The duration of the study could last up to 298 weeks (approximately 5.5 years). Subjects who complete, or who early terminate from the study will be contacted approximately 70 days after their last dose of study drug to obtain information on any ongoing and new adverse events (AEs). At study visits in addition to routine physical examination, laboratory assessments and calculation of the PMS and PUCAI, the following will be collected:

- Anthropometric evaluations at for determination of body mass index (BMI), and "z" scores for height and weight.
- IMPACT III Quality of Life questionnaire will be completed for subjects 9 years of age or older
- WPAI
- Tanner stage

This study will conclude approximately 12 weeks after one of the following criteria have been satisfied:

[figure not shown]

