The study will include an open-label period of approximately 298 weeks. Prior to Amendment 4, all subjects were minimally on open label 0.6 mg/kg (maximum of 40 mg) eow of adalimumab beginning at the Baseline visit. After Amendment 4, all subjects will be on open label 20 mg, 40 mg or 80 mg eow of adalimumab. A 70-Day Follow-Up phone call will be completed for all subjects who either terminate early from the study or who complete the study.

Criteria for Evaluation:

Efficacy:

This study will utilize the PMS (and Mayo score if available) and PUCAI to determine efficacy of the study drug.

The following efficacy endpoints will be analyzed using summary statistics:

- The proportion of subjects who achieve clinical remission as measured by PMS (defined as a PMS ≤ 2 and no individual subscore > 1) over time;
- The proportion of subjects who achieve clinical response as measured by PMS (defined as a decrease in PMS ≥ 2 points and ≥ 30% from Baseline) over time;
- The proportion of subjects who achieve PUCAI remission (defined as < 10) over time;
- The proportion of subjects who achieve PUCAI response (defined as a decrease in PUCAI ≥ 20 points from Baseline).

Efficacy will also be evaluated based on other measures of disease activity, including IMPACT III, WPAI, z-score for height and weight, bone age, BMI, and laboratory values as applicable. The proportion of subjects who achieve remission/response based on Mayo score and mucosal healing based on Mayo endoscopy subscore will be summarized for subjects with available Mayo score.

Pharmacokinetic and Immunogenicity:

As appropriate, population pharmacokinetic analysis and/or any additional analyses may be performed on samples for serum adalimumab concentrations and immunogenicity status collected prior to Amendment 2.

Adalimumab M10-870 Protocol Amendment 5 EudraCT 2015-001346-29

Criteria for Evaluation (Continued):

Safety:

Safety analyses will be performed on all subjects who receive at least one dose of study drug. Incidence of AEs, changes in vital signs, physical examination results, and clinical laboratory data will be assessed.

Statistical Methods:

[figure not shown]

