4.2 Design Diagram

This study is a Phase 3, multi-center, open-label study designed to evaluate the long-term maintenance of clinical response, safety and tolerability of ADA in pediatric subjects with ulcerative colitis.

Subjects are eligible to enroll in the Study M10-870 if they have successfully completed Protocol Study M11-290 through Week 52 and meet all of the inclusion criteria and none of the exclusion criteria for Study M10-870.

The Week 52 visit from the Study M11-290 serves as the Baseline Visit for subjects entering Study M10-870.

All subjects receive open-label therapy as follows beginning at the Baseline Visit in Study M10-870:

- Subjects who enroll into the study from blinded treatment in Study M11-290 receive open label 0.6 mg/kg (maximum of 40 mg) every other week (EOW) of adalimumab
- Subjects who received open label 0.6 mg/kg (maximum of 40 mg) every week (EW) of adalimumab in Study M11-290 maintain the same dose in Study M10-870

Subjects who demonstrate a disease flare may have their dose escalated. Subjects who have been in remission (PMS \leq 2 with no individual subscore > 1) for at least 8 weeks and for at least 2 consecutive visits may have their dosage de-escalated. Subjects who demonstrate disease flare after dose de-escalation have an opportunity to re escalate their dose back to adalimumab every week (EW) dosing.

[figure not shown]
Subjects with persistently uncontrolled disease while on adalimumab 40 mg EW (maximum dose) are to be discontinued from the study.

The duration of the study is up to 298 weeks (approximately 5.5 years).

More details are described in the protocol, including the Study Activities table.

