Partial Mayo Score	Composite score of UC disease activity based on the subscores of stool frequency, rectal bleeding, and physician's global assessment and DOES NOT include the endoscopic subscore. This score ranges from 0 – 9 points with higher scores representing more severe disease.	
9 point Mayo Score (without PGA)	Composite score of UC disease activity based on the subscores of stool frequency $(0-3)$, rectal bleeding $(0-3)$, and endoscopic subscore $(0-3)$. This score ranges from $0-9$ points with higher scores representing more severe disease.	
6 point Mayo Score (without PGA and endoscopy subscore)	Composite score of UC disease activity based on the subscores of stool frequency $(0-3)$ and rectal bleeding $(0-3)$. This score ranges from $0-6$ points with higher scores representing more severe disease.	

[figure not shown]

Table 2. Definition of Endpoints Based on Mayo Score and Component Scores

Term	Definition
Clinical remission per Partial Mayo Score	PMS ≤ 2 and no individual subscore ≥ 1
Clinical response per Partial Mayo Score	Decrease in PMS \geq 2 points and \geq 30% from Study M11-290-Baseline
Clinical remission per Mayo Score	Mayo score ≤ 2 and no individual subscore > 1
Clinical response per Mayo Score	Decrease in Mayo Score \geq 3 points and \geq 30% from Study M11-290-Baseline
Mucosal healing	Endoscopy subscore of 0 or 1
Clinical remission per 9 point Mayo Score (without PGA)	Defined as the 9 point Mayo Score (without PGA) \leq 2 and no individual subscore $>$ 1
Clinical remission per 6 point Mayo Score (without PGA and endoscopy subscore)	Defined as the 6 point Mayo Score (without PGA and endoscopy subscore) ≤ 1

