10.2 Efficacy Analysis

The efficacy endpoints are:

- The proportion of subjects who achieve clinical remission as measured by PMS (defined as a PMS ≤ 2 and no individual subscore ≥ 1) over time;
- The proportion of subjects who achieve clinical response as measured by PMS (defined as a decrease in PMS ≥ 2 points and ≥ 30% from Study M11-290-Baseline) over time;
- The proportion of subjects who achieve PUCAI remission (defined as < 10) over time;
- The proportion of subjects who achieve PUCAI response (defined as a decrease in PUCAI ≥ 20 points from Study M11-290-Baseline).
- Change from Baseline in total IMPACT III Quality of Life score and subscores over time for subjects at least 9 years old at Baseline;
- Change from Baseline in WPAI scores over time;
- Change from Baseline in "z" scores for height over time;
- Change from Baseline in BMI over time;
- Change from Baseline in "z" scores for weight-for-age over time;
- Change from Baseline in albumin and total protein over time;
- Change from Baseline in hemoglobin, hematocrit, red blood cell count over time;
- Change from Baseline in hs-CRP levels over time;
- Proportion of subjects at appropriate Tanner stage (see Section 6.0) over time;
- Proportion of subjects in Mayo score clinical response over time (for subjects with available Mayo score);
- Proportion of subjects in Mayo score clinical remission over time (for subjects with available Mayo score);
- Proportion of subjects who achieve mucosal healing over time as measured by Mayo endoscopy subscore (defined as ≤ 1, for subjects with available Mayo score)
- Proportion of subjects in 9 point Mayo score (without PGA) clinical remission over time (for subjects with available Mayo score);

• Proportion of subjects in 6 point Mayo score (without PGA and endoscopy subscore) clinical remission over time (for subjects with available Mayo score).

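### PMS remission is defined with ≥ 1 in the SAP and Protocol 5.3.2 but with > 1 in the synopsis and de-escalation text; as written, any child with a subscore of 1 counts as a non-remitter

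*SAP*

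**What the plan says.** Three places disqualify a child whose subscore is 1 or more:

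- SAP 6.0, Table 2: "PMS ≤ 2 and no individual subscore ≥ 1".
- SAP 10.2, first-listed efficacy endpoint: "defined as a PMS ≤ 2 and no individual subscore ≥ 1".
- Protocol 5.3.2, first-listed efficacy endpoint: the same wording as SAP 10.2.

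Elsewhere only a subscore above 1 disqualifies:

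- Protocol 1.2 (Synopsis), same endpoint: "defined as a PMS ≤ 2 and no individual subscore > 1".
- De-escalation text in the Protocol synopsis, 5.1 and 5.5.1: "2 with no individual subscore > 1) for at least 8 weeks". SAP 4.2 carries the same rule: "with no individual subscore > 1) for at least 8 weeks".
- SAP 6.0, Table 2, full Mayo remission: "Mayo score ≤ 2 and no individual subscore > 1". The 9-point Mayo row of that table uses the same cut.

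The SAP offers no rationale for a stricter PMS rule, and its Section 12.0 lists no changes.

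**The concern.** Each document contradicts itself: the protocol between its synopsis and Section 5.3.2, and the SAP between Section 4.2 and its Table 2 and Section 10.2. A programmer working from the SAP would implement ≥ 1, and the resulting rate would not be the synopsis endpoint.

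The endpoint carries weight. It is listed first among the efficacy endpoints, and PMS is scheduled at every clinic visit. It is also one of the two endpoints analysed across the nine subgroup factors in SAP 10.5; the other, full Mayo remission, depends on optional endoscopy. Protocol 8.1 frames the statistical objective around maintaining clinical remission, and the interim report described in Protocol 8.1.7 and SAP 4.4 supports a regulatory submission.

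There is also an internal inconsistency in the data. A child whose dose was reduced because of remission under the > 1 wording, with a subscore of exactly 1, would appear in the efficacy tables at that same visit as not in remission.

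**Working it through.** The plan states no figure for this point, so there is nothing to reproduce. The check compares the two rules over every score a child can have.

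**Inputs**

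- PMS is the sum of stool frequency (SF), rectal bleeding (RB) and PGA, with a range of 0 to 9 (SAP Table 1).
- Each daily SF or RB score and each PGA is a whole number from 0 to 3 (Protocol Appendix D).
- SF and RB for a visit are five-day averages kept as decimals (Protocol 5.3.1.1 and Appendix D; SAP 6.0). With a complete diary they move in steps of 0.2.

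**Five-day averages, > 1 rule** (PMS ≤ 2, every subscore ≤ 1)

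- PGA = 0: SF and RB each take 6 values (0, 0.2, …, 1.0), and their sum never exceeds 2. This gives 6 × 6 = 36.
- PGA = 1: SF + RB must be ≤ 1. This gives 6 + 5 + 4 + 3 + 2 + 1 = 21.
- Total: 36 + 21 = 57.

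**Five-day averages, ≥ 1 rule** (PMS ≤ 2, every subscore < 1)

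- PGA must be 0. SF and RB each take 5 values (0, …, 0.8). This gives 5 × 5 = 25.
- The highest PMS is 0.8 + 0.8 + 0 = 1.6.

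The difference is 57 − 25 = 32 combinations (32/57 = 56%). Of these, 21 have PGA = 1, and 36 − 25 = 11 have PGA = 0 with SF or RB exactly 1. These counts weight every combination equally and are not proportions of children.

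**Whole-number subscores:** 7 combinations qualify under > 1. Only one, all zeros, qualifies under ≥ 1.

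**Redundancy.** Under ≥ 1, PGA is 0 and SF and RB are each below 1, so PMS is below 2 in every case. The PMS ≤ 2 condition can never exclude anyone, so it would have no reason to be there.

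**Consistency with the other scores in Table 2.** Take SF 0, RB 0, PGA 1, endoscopy 1. The Mayo score is 2 with no subscore above 1, so the child is in full Mayo remission. The PMS is 1, but PGA is 1, so under ≥ 1 the child fails PMS remission, although PMS has fewer components. The 6-point remission row (score ≤ 1) also allows one subscore of 1, and mucosal healing allows an endoscopy subscore of 1. PMS remission is the only definition in the table that rejects a 1.

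**Illustration in children.** The 55 is the expected number outside Japan (SAP 4.3). The remission rate and the share with a subscore of exactly 1 are assumptions. Intervals are exact (Clopper-Pearson) 95% intervals.

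| Share of > 1 remitters with a subscore of exactly 1 | Remitters under ≥ 1 | Rate (95% CI) |
|---|---|---|
| 0% (same as the > 1 rule) | 28/55 | 51% (37 to 65) |
| 20% | 28 × 0.8 = 22.4, so 22/55 | 40% (27 to 54) |
| 40% | 28 × 0.6 = 16.8, so 17/55 | 31% (19 to 45) |
| 60% | 28 × 0.4 = 11.2, so 11/55 | 20% (10 to 33) |

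**The case against.** The point turns on one relational symbol, and such symbols can be corrupted when a document is converted; the disease-duration split in SAP 10.5 has a garbled sign in the copy examined. A check against the signed PDFs is reasonable. Corruption is an unlikely explanation, however: the same ≥ 1 appears in three places across two documents, while > 1 appears in other rows of the same table and in the matching synopsis sentence.

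Second, no endpoint is primary, no confirmatory testing is planned, and all results are descriptive (SAP 10.1 and 10.3). PMS response, both PUCAI endpoints and the Mayo endpoints are unaffected. This is correct and limits the damage to one family of results. It does not excuse two definitions: in an uncontrolled study the reported proportion is itself the efficacy finding.

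Third, the combination counts say nothing direct about children. Many remitters may score zero throughout, and averages such as 0.8 still qualify under ≥ 1. This stands. Only the direction is established; the size is not.

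Fourth, the correction is not purely typographical. One disease-flare criterion (Protocol synopsis, 5.1 and 5.5.1) depends on the child not being in PMS remission and does not say which definition applies. A protocol change also needs ethics committee approval (Protocol 9.1). Both points stand and affect how the correction is made, not whether it is needed.

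The SAP was written against Amendment 3, but that does not explain the conflict: Amendment 5 still disagrees with itself.

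**Conclusion.** The concern holds, and the definition must be corrected. The same endpoint has two incompatible definitions, nothing in either document reconciles or justifies them, and the one the SAP would have programmed makes its own PMS ≤ 2 condition inoperative. The internal evidence points to > 1 as the intended analysis definition.

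The ≥ 1 rate is never higher than the > 1 rate, and it is lower whenever a child who qualifies under > 1 has a subscore of exactly 1. Every qualifying child with PGA = 1 is lost. The amount cannot be fixed from the documents. The fall from 51% to between 40% and 20% rests on an assumed 28 of 55 remitters and an assumed 20% to 60% with a subscore of exactly 1. The conclusion also assumes that the printed symbols match the signed documents.

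**What to change.** Use one analysis definition of PMS remission throughout: PMS of 2 or less with no subscore above 1. This means changing ≥ 1 to > 1 in SAP Table 2, SAP 10.2 and Protocol 5.3.2; the synopsis already reads this way. If a stricter rule really was intended, state and justify it, and align the synopsis with it.

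Confirm the symbols against the signed PDFs and check that the derivation code matches. If any interim output used ≥ 1, rerun PMS remission and its subgroup tables and report the difference.

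The flare criterion that refers to PMS remission should be reconciled with the remission definitions elsewhere in the protocol; which clinical rule applies is for the sponsor to settle.

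The cost is one character in three places and a code check, with no new data. The SAP correction can be made on its own before database lock. The protocol correction carries the usual amendment approval and could be made with the next amendment.
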